No Intervention: “Do-as-usual” control group

Participants allocated to the control group are a "do-as-usual" comparator. This implies, that the participants may treat and prevent running-related pain and discomfort in any way they wish, except using the Zoles 3D-printed insoles.

Outcomes

Primary outcome

The primary outcome will be the change in running-related pain 10 weeks after baseline. Pain, although subjective, is a crucial determinant of runners' quality of life, performance, and continued participation in the activity [13]. For this trial, an 11-NRS pain scale will be utilized, ranging from 0 to 10 (0 = No pain at all, 10 = Worst pain imaginable) [48].

Baseline values for the primary outcome will be collected using online e-mail-distributed surveys via REDCap (Vanderbilt University, Nashville, TN, USA). Running-related pain data will be further collected at weekly intervals, with the focal analysis being between-group changes from baseline to the 10-week mark. The main outcome will be reported as the difference in mean change in running-related pain between the group using Zoles customised 3D-printed insoles and the "do-as-usual" control group, adjusting for values reported at baseline [49].

Secondary outcomes

The secondary outcomes include:

- **Global Rating of Change (GRoC) in overall daily pain and discomfort:** Participants will be asked to self-assess their perceived change in overall daily pain and discomfort relative to their state at the start of the study. They will use a 7-point scale, from -3 ("much worse") to 3 ("much better"), as indicated in the study by Bobos et al. [36] This outcome will be measured weekly until the 10-week mark, and again at the 18-week mark.
- **Running-related foot/footwear comfort:** The change in comfort from the start to the 10-week mark, relating specifically to running and footwear, will be captured using a numeric rating scale ranging from 0 (Extremely uncomfortable) to 10 (Extremely comfortable) based on the parameters defined by Menz & Bonnano [37]. This outcome will be measured at baseline with weekly follow-up measurements until the 10-week mark, and again at the 18-week mark.

- **5k-completion time:** The time taken by participants to complete their weekly 5 km parkrun will be recorded weekly, providing insights into any performance changes over the trial period.

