In adherence to transparency and scientific scrutiny, a fully anonymised dataset at the participant level, accompanied by the corresponding statistical code, will be made available to the public, contingent upon the requirements of the journal publishing the study's findings. This disclosure ensures the replicability and verification of the research while upholding the anonymity and privacy of all participants.

The published results will omit any information that could potentially be used to identify individual participants.

Statistical methods

The primary outcome; change in running-related pain from baseline to follow-up, will be calculated using negative binomial regression. Figure 4 illustrates a hypothetical change in pain over the course of the trial, including the expected catch-up by the control group at week 18. It is important to note, however, that the between-groups analysis for difference will adjust for

values reported at baseline [49,57]. Both the Global Rating of Change (GROC) in overall daily pain and discomfort and running-related foot/footwear comfort will be calculated similarly. Injury incidence rate ratios will be estimated per 1000 hours of running exposure using Poisson regression. Mean time-loss from running will be calculated using negative binomial regression. Adherence to the intervention will be descriptively analysed and presented, and adverse event due to the Zoles insoles will be presented in type and frequency. Every analysis in the main trial report will abide by the intention to treat principle, which means including all participants in the analyses, regardless of intervention adherence-signifying that participants will be analysed based on initial randomisation. In the primary trial report, all collected outcomes will be listed, and it will also be stated that the below-mentioned 'other pre-specified outcomes' will be reported in a subsequent secondary analysis publication with a clear reference to the primary trial registration.

Possible effect modifiers include time with allocated intervention due to possible logistics issues in handing over the insoles to the intervention group, as well as any last-minute needs for sizing adjustments if a pair of insoles do not fit inside a participant's footwear. Any new injury sustained during the trial period is another potential effect modifier. No potential external effect modifiers will be factored in the intention-to-treat analyses.

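### Negative binomial regression is assigned to signed outcomes: it cannot be fitted to GRoC as coded, and for pain and comfort the response, link and step to the promised mean difference are not stated

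*Combined protocol and SAP*

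**What the plan says.** All references are to the combined protocol and SAP.

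- **Statistical methods, primary outcome:** "The primary outcome; change in running-related pain from baseline to follow-up, will be calculated using negative binomial regression". The same paragraph adds that "the between-groups analysis for difference will adjust for" baseline values. It gives no link function and does not name a dependent variable separately from the change.
- **Statistical methods, GRoC and comfort:** "Both the Global Rating of Change (GROC) in overall daily pain and discomfort and running-related foot/footwear comfort will be calculated similarly".
- **Outcomes, primary outcome:** pain is scored 0 to 10, the focal time point is week 10, and "The main outcome will be reported as the difference in mean change in running-related pain" between the groups, adjusted for baseline.
- **Outcomes, GRoC:** the coding is signed: "They will use a 7-point scale, from -3" at the worst end, with +3 as the best rating. The rating is also comparative in itself, since each participant is asked to "self-assess their perceived change in overall daily pain and discomfort relative to their state at the start of the study".
- **Outcomes, comfort:** the outcome is "The change in comfort from the start to the 10-week mark" on a 0 to 10 scale. "This outcome will be measured at baseline with weekly follow-up measurements until the 10-week mark", so a baseline value exists.
- **Statistical methods, secondary subgroup analysis:** participants with baseline pain of 3 or more are analysed in the same way as the primary outcome.

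**The concern.** A negative binomial model assigns probability only to 0, 1, 2 and so on. A single negative value leaves its likelihood undefined. A change between two 0-10 scores runs from -10 to +10, and the trial's own hypothesis is that pain falls. GRoC is signed by construction.

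This sentence is the plan's only specification of the primary model. If it is taken literally, the analyst has to replace the stated response. If it is taken as a model of the week-10 score, the analyst has to supply a link and a conversion to reach the additive effect that the Outcomes section promises. Either way, choices about the primary analysis are left open in a trial with unblinded participants and a self-reported primary outcome. They are best fixed before anyone sees data by group.

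**Working it through.** **Inputs from the Sample size section.** Median pain 3, IQR 2-5, so SD = 3/1.35 = 2.22, as the plan states. The effect is 40% of 3 = 1.2 points, also as stated. With these inputs the plan's formula gives (1.960 + 0.842)² × 2 × 2.22² / 1.2² = 53.7, or 54 per group rather than the stated 70. That is a separate matter, and nothing here depends on it.

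**Assumption.** The documents give no correlation between baseline and week-10 pain, so a range of 0.3 to 0.7 is used.

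**Step 1: GRoC.** No simulation is needed. The categories are -3, -2, -1, 0, 1, 2, 3, and three of the seven are negative. Each rating is already relative to the start of the study, so there is no baseline GRoC to serve as a covariate.

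**Step 2: pain change as the response.** Hand approximation at correlation 0.5: the SD of change is 2.22 × √(2 × (1 − 0.5)) = 2.22. A whole-point fall corresponds roughly to a change below -0.5.

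- Control (mean change 0): Φ(−0.5/2.22) = Φ(−0.23) ≈ 41%.
- Intervention (mean change −1.2): Φ((−0.5 + 1.2)/2.22) = Φ(0.32) ≈ 62%.

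Simulation with scores rounded and clipped to 0-10 (400,000 per arm) gives slightly lower shares at this correlation, 40% and 59%, because clipping at 0 creates ties. Over correlations 0.3 to 0.7:

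| Share of pain changes below zero | Intervention | Control |
|---|---|---|
| Follow-up minus baseline | 58-61% | 37-41% |
| Sign reversed | 15-25% | 37-42% |
| Baseline ≥ 3 subgroup | 76-77% | 49-59% |
| Baseline ≥ 3 subgroup, sign reversed | 10-12% | 26-28% |

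The normal shape is not critical. A skewed 0-10 baseline distribution with quartiles 2, 3 and 5 and a 40% proportional reduction gives 64-68% and 37-42% (reversed: 10-19% and 38-42%). Reversing the sign of the change therefore does not help.

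**Step 3: week-10 pain as the response, baseline as covariate.** This model fits. It was compared with ANCOVA, both with robust standard errors, at 100 complete participants per arm (2,000 null and 1,000 alternative replicates):

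| | Negative binomial | ANCOVA |
|---|---|---|
| Type I error, correlation 0.3 | 5.0% | 5.1% |
| Type I error, correlation 0.6 | 4.8% | 5.6% |
| Power at 1.2 points, correlation 0.3 | 98% | 98% |
| Power at 1.2 points, correlation 0.6 | 99.7% | 99.8% |
| Power at 0.8 points (assumed), correlation 0.3 | 72% | 72% |
| Power at 0.8 points (assumed), correlation 0.6 | 85% | 86% |

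**Step 4: effect scale.** Clipping at 0 shrinks the 1.2-point shift to arm means of 2.06 and 3.09, a difference of −1.03. With a log link the model reports a ratio of 0.67 (2.06/3.09). Only after standardising over the sample does it give −1.04 points, against −1.03 from ANCOVA. The ratio alone does not fix the difference. A ratio of 0.6 means −0.4 × the control mean: −0.4 points at a control mean of 1, −1.2 at 3 and −2.8 at 7.

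**The case against.** The strongest reply is that the sentence describes what is estimated, not what is modelled. The same paragraph says that mean time-loss will be calculated by negative binomial regression, and a mean is what a fitted model yields, not a response variable. Read in parallel, change in pain is the estimand, and the baseline adjustment points to a model of the week-10 score. A repeated-measures model of the weekly scores would also have a non-negative response. Week 10, the effect measure and the baseline adjustment are all stated in the Outcomes section.

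Much of this stands. The week-10 reading is plausible for pain and comfort, so the claim that the model cannot be fitted holds for them only on the literal reading. The objection does not supply the missing pieces, though. Nowhere is the week-10 score (or the series of weekly scores) named as the dependent variable, and neither a link nor a conversion to a mean difference is given. Nor does it help GRoC, which is signed and without a baseline value on any reading unless it is recoded.

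A reader might infer from this point that the primary analysis is impossible to run or statistically invalid, or that the trial loses power. The documents do not support that. On the workable reading the two models agree closely for pain. Nor is negative binomial regression in question for days of time-loss, which are non-negative counts.

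**Conclusion.** The plan is wrong as written for GRoC: the named model cannot be fitted to a -3 to +3 scale without recoding, and there is no baseline GRoC to adjust for. For pain and comfort it is unfittable on the literal reading and under-specified on the plausible one. The ambiguity carries over to the subgroup with baseline pain of 3 or more. Because the primary outcome is affected, this should be settled before analysis, although the demonstrated harm for pain is limited to ambiguity and a ratio in place of the promised difference.

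The GRoC conclusion rests on the scale definition alone. The pain percentages rest on the plan's mean, SD and effect, the assumed correlations, and rounding and clipping to 0-10. The close agreement between models was shown for pain with 100 complete participants per arm, without the plan's 15% dropout. Comfort was not simulated.

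**What to change.** In Statistical methods:

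1. Name the week-10 pain and comfort scores, not the change, as the response, with the baseline score as covariate.
2. State one of two models. (a) Linear ANCOVA with robust standard errors, reporting the adjusted mean difference and 95% CI. With baseline as a covariate, the group coefficient is the same whether week-10 score or change is the response, so this gives the promised measure directly. (b) Negative binomial regression with a stated link, robust standard errors and a standardised marginal mean difference with 95% CI. For pain either is acceptable on the figures above; (a) needs fewer steps.
3. Give GRoC its own model, either proportional-odds or linear with robust standard errors, without a baseline GRoC term.
4. Apply the corrected pain model to the subgroup with baseline pain of 3 or more.

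The time-loss model can stay. The cost is wording only, with the same data, design and sample size. The change can be recorded by the route for protocol modifications in Ethics and dissemination.

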The allocation phase (Timepoint 0) commences post-enrolment, where participants are sent a baseline questionnaire. The information gathered from this questionnaire is used in the balanced block randomisation procedure. Upon completion of the baseline questionnaire, participants are set up to receive weekly follow-up surveys during the primary study period (Weeks 1-10). During this period, there is weekly follow-up on primary and secondary outcomes, delivery of allocated intervention group insoles projected before week 3, and weekly monitoring of adherence and adverse effects. In a case where a pair of insoles do not fit inside a participant's footwear, a fast-track adjustment, production, and shipment procedure takes place, ensuring a minimal delay of insole delivery of approximately one week.

In the control group step allocation period (Weeks 10-18), control group participants receive their customised insoles and all participants are sent a single event follow-up questionnaire at week 18. This questionnaire covers primary and secondary outcomes, as well as adherence and adverse effects.

Finally, post-market surveillance occurs at Timepoint Week 52, a year after the study's commencement. All participants receive a follow-up questionnaire assessing their post-trial experiences with the insoles, any adverse effects experienced during the year, and the long-term effects of the Zoles insoles (Figure 3).

Sample size

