Specifically, the block randomisation will be stratified by sex and the specific parkrun location from which participants were recruited. This stratification ensures that each comparison group will have a representative mix of participants based on these two key variables, pre-hypothesised as potential confounders, allowing for a more controlled comparison of outcomes, and to improve external validity and generalisability of the results [51].

The process of generating the allocation sequence will be undertaken by an external who is not involved in any aspect of the trial to improve the integrity and credibility of the allocation process, as recommended [52]. The dataset provided for randomisation will only contain participant number, local parkrun location, and sex. The data will be initially separated by sex, and within each gender group, a stratification variable will be created based on local parkrun location. Block randomisation, with a block size of 4, will be conducted separately for males and females within each stratum (location) using a custom script developed in R. This approach ensures an equal or near-equal distribution of males and females within each treatment group across all locations. The randomisation process within each stratum will be automated through the script, and the resulting group assignments will be merged back into the original dataset. The R script used for the randomisation will be available as supplementary material to the primary trial report. Once the allocation sequence is generated, participants will be informed of their respective group assignments, either the intervention group (receiving the ZOLEs insoles) or the control group ("do-as-usual").

Blinding

Given the pragmatic nature of this trial, participants are not blinded to their group allocation. The absence of a sham insole for distribution means that participants will be aware of whether they are in the intervention group (receiving the ZOLEs insoles) or the control group ("do-as-usual"). Despite this, the allocation process remains concealed, ensuring that neither participants nor researchers are aware of the allocation sequence until the appropriate intervention shall be administered. This measure is in place to prevent any potential biases that might arise from foreknowledge of group assignments [53,54]. To further the study's integrity, we will use an external outcome assessor that is blinded to group assignments [55].

Procedures and data collection

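### The primary pain model does not name the stratification factors, sex and parkrun location, so its confidence interval may be slightly too wide (low priority)

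*Combined protocol and SAP*

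**What the plan says.** Allocation states that "the block randomisation will be stratified by sex and the specific parkrun location from which participants were recruited", in blocks of four, and describes the two variables as "pre-hypothesised as potential confounders". Both appear again as predictors in the multiple-imputation model (Statistical methods – analysis population and missing data).

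For the primary comparison, Primary outcome speaks of "adjusting for values reported at baseline". Statistical methods repeats this for the negative binomial model: "It is important to note, however, that the between-groups analysis for difference will adjust for" the baseline values. No section puts sex or location into an outcome model.

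The natural reading of the baseline phrase is the pain score itself, because Primary outcome also says "Baseline values for the primary outcome will be collected using online e-mail-distributed surveys via REDCap". That reading is not certain. Participant timeline says of the baseline questionnaire: "The information gathered from this questionnaire is used in the balanced block randomisation procedure". Sex and location may therefore be reported on that form too, and its content (Appendix F) is listed but not reproduced.

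**The concern.** Stratified blocks keep the two groups nearly balanced on sex and location. If these factors predict week-10 pain beyond baseline pain, that balance removes some chance variation from the estimated group difference. A model without the factors leaves their variation in the residual. Its standard error then ignores a gain in precision that the design has already delivered.

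What is at stake is a small loss of reported precision on the primary outcome, and a covariate list for the primary model that can be read in two ways.

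**Working it through.** **Inputs from the documents (Sample size).** Mean pain 3, SD 2.22, difference 1.2 points, two-sided 5%, 100 per group, 15% dropout, which leaves 85 per group.

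**Assumed, because the documents do not give them.** R² is the share of pain variance left after baseline pain that sex and location explain (0 to 10%). r is the correlation of baseline with week-10 pain. The number and size of locations are also assumed.

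**1. The plan's own figures.** The SD reproduces: (5 − 2)/1.35 = 2.22. The stated 70 per group does not. The printed formula gives (1.96 + 0.84)² × 2 × 2.22²/1.2² = 53.7, so 54. That is a separate matter, and nothing below uses the 70.

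**2. Linear approximation.**
- Reported SE = 2.22 × √(1 − r²) × √(2/85).
- Earned SE = reported SE × √(1 − R²), so excess width = 1/√(1 − R²) − 1.
- Power with strata terms = Φ(1.2/earned SE − 1.96).
- Power without = Φ(1.2/earned SE − 1.96/√(1 − R²)).

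| R² | Excess width | Actual type I error without strata terms |
|---|---|---|
| 0 | 0% | 5.0% |
| 2% | 1.0% | 4.8% |
| 5% | 2.6% | 4.4% |
| 10% | 5.4% | 3.9% |

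At R² = 10%:

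| r | 95% half-width, reported vs earned (NRS points) | Power, without vs with strata terms |
|---|---|---|
| 0 | 0.667 vs 0.633 | 95.0% vs 96.0% |
| 0.3 | 0.637 vs 0.604 | 96.6% vs 97.3% |
| 0.5 | 0.578 vs 0.548 | 98.7% vs 99.0% |

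The lowest power in this range is 94.1% (r = 0, R² = 0). These figures give the scale in NRS points, but the planned model is not linear.

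**3. Planned model: negative binomial, baseline pain included, no treatment effect, blocks of four within sex-by-location.** The strata terms lower the maximum-likelihood SE by about 1% even when they predict nothing. The net excess is therefore the ratio of SEs (without/with strata terms) divided by the same ratio at R² = 0.

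First set: 2,000 trials per setting, 170 analysed, five locations at 60/15/10/10/5%, over-dispersed count capped at 10.
- Observed correlation 0.22: 1.0371/1.0095 gives 2.7% at R² 5.1%, and 1.0692/1.0095 gives 5.9% at R² 10.3%.
- Observed correlation about 0.44: 1.0259/1.0110 gives 1.5% at R² 2.6%, and 1.0409/1.0110 gives 3.0% at R² 5.0%.

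Second set: about 172 analysed.
- r = 0.3: 2.6% at R² 5% and 5.7% at R² 10%.
- r = 0.5: 1.5% at R² 5% and 3.0% at R² 10%.

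Together these give roughly 1.5–3% at R² 5% and 3–6% at R² 10%.

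**4. Where the effect vanishes.** A negative binomial variance cannot fall below its mean. With mean 3 and residual variance 2.22² × (1 − r²) = 4.93 × (1 − r²), the two are equal at r = √(1 − 3/4.93) ≈ 0.63. Above that the fit collapses to Poisson, whose model-based variance depends on the mean and not on the residual spread. At r = 0.7 the estimated dispersion was zero in 98–100% of simulated trials, and leaving the strata out added no width. The boundary uses the baseline mean and SD, and it moves if week-10 values differ.

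**5. Reported SE or true spread?** In the first set at R² of about 5%, the trial-to-trial spread of the estimate was the same without and with strata terms (0.1350 vs 0.1358; 0.1255 vs 0.1253). Only the reported SE changes.

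**6. False positives in the first set.** With R² above 0, type I error was 3.8–5.2% without strata terms and 4.4–5.8% with them. At R² = 0 it was 6.7% vs 6.7% in one setting and 4.9% vs 5.7% in the other (Monte Carlo SE about 0.5 points). The 6.7% is the same either way, so the omission does not cause it.

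**7. Other outcomes.**
- Comfort, with an assumed mean and SD of 7 and 2, or 6 and 2.2: the variances of 4 and 4.84 lie below the means, so the dispersion collapses to zero. SE ratios for these comfort settings and for pain at r = 0.7 were 0.994–0.998, so there is no excess.
- Injuries by Poisson regression, with about 0.25 injuries per participant assumed: median model-based SE 0.304–0.312 without strata terms and 0.305–0.314 with them.

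**The case against.** **The effect may be close to nothing.** Study setting says recruitment was mainly from one park, so location may vary little, and baseline pain already absorbs stable differences between the sexes. If sex alone (split 50:50) carried the R² at r = 0.5, the residual SD would be 1.92. R² of 2, 5 and 10% would then need male–female differences of 2 × 1.92 × √R² = 0.54, 0.86 and 1.2 points beyond baseline. The last equals the whole forecast treatment effect. This stands: the low end of the range is the more plausible.

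**The plan may already include the factors.** The baseline phrase is unspecific, and the questionnaire feeds the randomisation. This stands as uncertainty, and it is itself a reason to list the covariates.

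**The plan rules out other factors.** Statistical methods keeps external effect modifiers out of the intention-to-treat analyses. That sentence follows a list of post-randomisation items (time with the insole, sizing adjustments, new injury), so it does not clearly cover stratification factors as main effects.

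**A reader might extend the point to comfort**, because "running-related foot/footwear comfort will be calculated similarly". The planned model does not support that. A 0–10 comfort score with a middling or high mean is likely under-dispersed, and its negative binomial interval is then not widened by leaving the strata out. For the same reason the linear percentages cannot be carried over to every baseline correlation for pain.

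**Conclusion.** The point holds for the primary pain model only, as a low-priority efficiency and clarity matter. If sex and location predict week-10 pain beyond baseline pain, the reported interval is too wide by roughly 1.5–3% (R² 5%) or 3–6% (R² 10%) at baseline correlations of about 0.2 to 0.5. There is no excess if R² is zero, or if the correlation is above roughly 0.6 given the plan's mean and SD. R², the correlation and the mix of locations are all assumed.

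Because the plan calls the factors potential confounders, a reader might infer that leaving them out biases the comparison or undermines the trial. The documents do not support that. Randomisation within these strata balances the groups on them, the error runs towards caution, and power for 1.2 points remains at 94% or more in the linear approximation. No excess width is claimed for comfort, global rating of change, time-loss or injuries.

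**What to change.** In Statistical methods, name sex and recruitment location as covariates, alongside baseline pain, in the primary pain model. Add a rule for pooling sparse locations, set before group labels are revealed to the analyst. The same list may be used for the other outcomes for consistency, without claiming a gain in precision. If the baseline phrase already covers these factors, or if they are left out on purpose, one sentence saying so is enough.

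The cost is a covariate list and a pooling rule. No new data are needed, since Allocation puts both factors in the randomisation dataset. The downsides are a few degrees of freedom (with five locations, for example, 1 for sex and 4 for location, out of about 170; the number of locations is not stated), possibly unstable terms for small locations, and the fall of about 1% in the negative binomial SE from the extra terms alone.
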